ClinicalTrials.gov Study Protocol

Official Title: Diastolic Dysfunction in the Pregnant Woman with Preeclampsia: A Prospective Observational Study at the Maternity and Neonatology Center of Tunis

Short Title: Diastolic Dysfunction in Preeclampsia

NCT Number: [to be assigned]

Date: August 2025

Sponsor/Responsible Party: Maternity and Neonatology Center of Tunis

Principal Investigator: [DR [name], MD, Maternity and Neonatology Center of Tunis, Tunisia, [contact]]

1. Objective

The objective of this study is to evaluate diastolic function in pregnant women with preeclampsia and to compare findings with normotensive pregnant women.

2. Study Design

- Study Type: Observational (Case-Control)
- Study Model: Case-Control, two cohorts (Preeclampsia vs. Normotensive)
- Time Perspective: Prospective
- Enrollment: 80 participants (40 in each cohort)
- Follow-up Duration: Until delivery and immediate postpartum (up to 7 days)

3. Study Setting and Duration

This study was conducted within the Anesthesia-Resuscitation and Gynecology-Obstetrics Departments (A, B, C, and D) of the Maternity and Neonatology Center in Tunis, Tunisia, over a 5-month period from March 2025 to June 2025.

4. Eligibility Criteria

Inclusion Criteria:

- Pregnant women aged 18–45 years
- Third trimester of pregnancy
- Group A: women diagnosed with preeclampsia ($\geq 140/90$ mmHg after 20 weeks + proteinuria ≥ 300 mg/24h, with or without severity criteria)
- Group B: normotensive pregnant women without proteinuria (< 300 mg/24h if tested)

Exclusion Criteria:

- Pre-existing cardiovascular disease (valvulopathy, cardiomyopathy, EF $< 50\%$)
- Congenital heart disease, arrhythmia, prior cardiac surgery
- Chronic hypertension (before 20 weeks)
- Pulmonary hypertension (pre- or post-capillary)
- Systemic disease with cardiac involvement (SLE, Behçet's disease)
- Technical difficulty preventing echocardiographic evaluation
- Unusable medical records or diagnostic uncertainty
- Gestational hypertension without preeclampsia

5. Study Procedures

Data Collection:

- Demographics, medical history, clinical and biological data collected using standardized forms.
- Echocardiographic parameters recorded according to ASE/EACVI 2016 guidelines.

Echocardiographic Parameters Assessed:

- Transmitral Doppler flow (E wave, A wave, E/A ratio, Deceleration Time)
- Tissue Doppler imaging (E' septal, E' lateral, A', S')
- Indexed left atrial volume
- Maximum tricuspid regurgitation velocity (Vmax TR)

Classification of Diastolic Function:

- Normal
- Indeterminate
- Diastolic Dysfunction (Grade I = impaired relaxation; Grade II = pseudonormal; Grade III = restrictive)

6. Outcome Measures

Primary Outcome:

- Title: Prevalence of left ventricular diastolic dysfunction in preeclamptic women
- Description: Echocardiographic evaluation based on ASE/EACVI 2016 criteria
- Time Frame: At echocardiographic evaluation during the third trimester

Secondary Outcomes:

1. Comparison of diastolic parameters between preeclamptic and normotensive groups (E', E/E', LA volume, TR velocity).
2. Association between diastolic dysfunction and maternal symptoms (dyspnea, palpitations, pulmonary edema).
3. Correlation between severity of preeclampsia and degree of diastolic dysfunction.

- Time Frame: During pregnancy and up to 7 days postpartum.

7. Statistical Analysis Plan

- Continuous variables expressed as mean \pm SD; compared using Student's t-test or Mann-Whitney U test.
- Categorical variables expressed as counts (%) and compared using Chi-square or Fisher's exact test.
- $p < 0.05$ considered statistically significant.
- Subgroup analysis: association between severity of preeclampsia and prevalence of diastolic dysfunction.

8. Ethical Considerations

- Study approved by the Local Ethics Committee of the Maternity and Neonatology Center of Tunis.

- Written informed consent obtained from all participants.
- Confidentiality, anonymity, and protection of personal data ensured.

9. References

ASE/EACVI 2016 Guidelines on Diastolic Function.

Melchiorre K et al. Circulation. 2011.

Guirguis G et al. J Am Soc Echocardiogr. 2015.

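### Secondary outcome 2 (dysfunction and symptoms) names no analysis population; if both groups are pooled, the planned crude test can be confounded by preeclampsia

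*Combined protocol and SAP*

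**What the plan says.** Section 6 defines secondary outcome 2 in one line: "Association between diastolic dysfunction and maternal symptoms (dyspnea, palpitations, pulmonary edema"). It names no population. The neighbouring outcomes are clearer. The primary outcome is "Prevalence of left ventricular diastolic dysfunction in preeclamptic women", and secondary outcome 1 is "Comparison of diastolic parameters between preeclamptic and normotensive groups". Secondary outcome 3 concerns the severity of preeclampsia, so it can only refer to Group A.

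Section 7 is the whole analysis plan. For categorical data it says "Categorical variables expressed as counts (%) and compared using Chi-square or Fisher's exact test", and continuous data are "compared using Student's t-test or Mann-Whitney U test". It contains no stratification, regression, matching or other adjustment. Its one subgroup analysis relates severity to dysfunction and does not involve symptoms.

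Section 2 fixes the sample by preeclampsia status: "Enrollment: 80 participants (40 in each cohort"). Section 1 has diastolic function evaluated in both groups, so a table of all 80 women can be built and nothing excludes it.

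**The concern.** The 1:1 split between preeclamptic and normotensive women is set by the design. A pooled table of dysfunction against symptoms therefore combines two deliberately selected groups. If Group A has more dysfunction and, for other reasons, more symptoms, the pooled table shows an association even when there is none inside either group. The first of these conditions is the difference that the study sets out to look for. The second is plausible but not stated.

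A significant crude result could then be read as a link between dysfunction and symptoms when it shows only that preeclamptic women have more of both. The plan gives the reader no way to tell the two apart, or even to know which women are in the table.

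**Working it through.** **Figures in the plan.** There is none to reproduce for this outcome: the documents give no dysfunction rate, symptom rate, effect size or power. The only inputs taken from them are 40 women per group (Section 2), chi-square or Fisher tests and a 0.05 threshold (Section 7). I took the test as two-sided. All rates below are assumptions, and dysfunction is treated as yes/no.

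**Pooled odds ratio with no association inside either group.** Let dysfunction have frequency pA and pB, and the symptom sA and sB, in Groups A and B. The expected pooled cells are:

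- a (both) = 40(pA·sA + pB·sB)
- b (dysfunction only) = 40[pA(1−sA) + pB(1−sB)]
- c (symptom only) = 40[(1−pA)sA + (1−pB)sB]
- d (neither) = 40[(1−pA)(1−sA) + (1−pB)(1−sB)]

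The pooled odds ratio is ad/bc.

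Example, both 40% v 10%:

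- a = 40(0.16 + 0.01) = 6.8
- b = c = 40(0.24 + 0.09) = 13.2
- d = 40(0.36 + 0.81) = 46.8
- odds ratio = 6.8 × 46.8 / 13.2² = 318.24 / 174.24 = 1.83

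Stratified by group, the same expected counts give (6.4 × 14.4 + 0.4 × 32.4) / (9.6² + 3.6²) = 105.12 / 105.12 = 1.00, the true value.

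**Rejection rates.** I used 20,000 simulated studies per setting, with chi-square without continuity correction.

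| Dysfunction, A v B | Symptom, A v B | Pooled OR | Chi-square | Fisher |
|---|---|---|---|---|
| 20% v 10% | 20% v 10% | 1.16 | 5.6% | 3.4% |
| 30% v 10% | 30% v 10% | 1.44 | 10.5% | 7.3% |
| 40% v 10% | 40% v 10% | 1.83 | 20.9% | 16.2% |
| 50% v 10% | 50% v 10% | 2.38 | 40.9% | 35.0% |
| 40% v 10% | 40% v 30% | 1.19 | 6.7% | 4.9% |
| 30% v 10% | 10% v 1% | 1.62 | 10.8% | 5.3% |
| 40% v 10% | 20% v 20% | 1.00 | about 5% | 3-4% |
| 40% v 40% | 40% v 10% | 1.00 | about 5% | 3-4% |

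Over all ten null settings run, which include these eight, the Mantel-Haenszel test stratified by group rejects 3.8-5.3% of the time. Its exact conditional version rejects 1.8-3.7%.

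**Cost in power.** Here dysfunction is 40% v 10%, and symptom frequency depends on dysfunction in the same way in both groups, so there is no confounding.

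| Symptom, with v without dysfunction | Mantel-Haenszel, 80 women | Pooled chi-square, 80 women | Chi-square, Group A only |
|---|---|---|---|
| 40% v 20% | 37% | 44% | 29% |
| 50% v 20% | 66% | 73% | 52% |

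**Precision in Group A alone.** With 16 women with dysfunction and 24 without, the 40% v 20% case gives expected cells 6.4, 9.6, 4.8 and 19.2.

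- odds ratio = 6.4 × 19.2 / (9.6 × 4.8) = 2.67
- Woolf standard error of its log = √(1/6.4 + 1/9.6 + 1/4.8 + 1/19.2) = 0.72
- 95% CI = exp(0.98 ± 1.96 × 0.72), about 0.6 to 11

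The 50% v 20% case gives cells 8, 8, 4.8 and 19.2, an odds ratio of 4.0 and a CI of about 1.0 to 16.

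**The case against.** The documents establish only an omission. Bias needs three things they do not state: pooling, a group difference in dysfunction, and a group difference in symptoms. A Group A reading has textual support, since the title, the primary outcome, secondary outcome 3 and the only subgroup analysis all centre on preeclampsia. If that is the intention, the confounding by group disappears and one clarifying phrase is enough. This is fair, but the objective covers both groups and nothing limits outcome 2 to Group A.

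The large error rates also require both features to be four or five times as frequent in Group A. A symptom common in normotensive women produces little inflation (6.7% by chi-square at 40% v 30%). That stands, and it is why the size is given as a range. For rare symptoms, Fisher's test keeps rejections near nominal. That also stands, but the pooled odds ratio remains biased (1.62 in the rare-symptom setting), and Section 7 gives no rule for choosing between the two tests.

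Finally, Mantel-Haenszel is one of several acceptable adjustments, and Group B may contribute little: at an assumed 10% it has 40 × 0.10 = 4 women with dysfunction, too few to check that the odds ratio is common to both groups. The outcome is also secondary and makes no causal claim. These points limit the weight of the concern but do not justify leaving a pooled crude test unqualified.

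**Conclusion.** The concern holds, in conditional form. It is certain that secondary outcome 2 names no population and that only crude tests are planned. The confounding arises only if the 80 women are pooled and both dysfunction and symptoms differ by group. Under assumed rates with no true association, the pooled odds ratio then runs from 1.16 to 2.38 and chi-square rejection from 5.6% to 40.9%. There is no bias if only one feature differs by group, and none from group membership if only Group A is analysed. The documents cannot place the study within this range. The primary outcome is unaffected. This is an inexpensive improvement that should be made, not a flaw that undermines the study.

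**What to change.** State the population for secondary outcome 2.

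- **If all 80 women:** use a Mantel-Haenszel test stratified by group, in its exact conditional form if cells are sparse. Report the common odds ratio with its 95% CI and show the Group A table beside it. Do not interpret a crude pooled result as an association between dysfunction and symptoms. Logistic regression with a group term (exact or penalised if sparse) would also serve.
- **If Group A only:** say so. Stratification by group is then unnecessary. Report it with confidence intervals, because 40 women give an imprecise answer.

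In either case, name the yes/no split of the diastolic classes, including where the indeterminate class goes.

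No new data are needed, since group is already recorded. The document is dated August 2025, after the stated study period of March to June 2025, so this should be recorded as a dated analysis change. Stratifying costs about 7 percentage points of power in the settings examined (37% against 44%, and 66% against 73%). Neither route removes confounding by severity within Group A.

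### Secondary outcome 1 compares disease-defined groups, with no matching described, by unadjusted tests only; a difference in maternal age or gestational age at scan could be misread as linked to preeclampsia

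*Combined protocol and SAP*

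**What the plan says.** Section 1 sets out to evaluate diastolic function in preeclampsia and "to compare findings with normotensive pregnant women". Section 2 describes the design as "Case-Control, two cohorts (Preeclampsia vs. Normotensive)" with "80 participants (40 in each cohort)". Section 4 gives both groups the same limits on age ("Pregnant women aged 18–45 years") and gestation ("Third trimester of pregnancy"), and the same cardiac, pulmonary-hypertension, systemic-disease and chronic-hypertension exclusions. Controls are otherwise defined only by normal blood pressure and absence of proteinuria. No matching factor is named.

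Secondary outcome 1 in Section 6 is "Comparison of diastolic parameters between preeclamptic and normotensive groups", covering E', E/E', LA volume and TR velocity. Its analysis is the Section 7 line for continuous variables, "compared using Student's t-test or Mann-Whitney U test", judged at p<0.05. The only other analysis listed concerns preeclampsia severity and prevalence of dysfunction. It does not adjust this comparison. The time frame under the secondary outcomes runs to 7 days after delivery, whereas the primary outcome is tied to a third-trimester scan.

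**The concern.** Without randomisation, a significant test says that the group means differ; it does not say why. Shared eligibility narrows the room for imbalance but leaves a 27-year age span (45 − 18) and the whole third trimester. If the preeclamptic women are older, or are scanned at a different week, and a parameter varies with that covariate, some or all of the observed difference comes from the covariate. Nothing in Section 7 would show this. At stake is how the between-group echocardiographic comparison is read, which is the second half of the stated objective.

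**Working it through.** The plan states no power, SD or expected difference, so there is no figure of its own to reproduce.

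**Inputs.** From the documents: 40 per group and a 0.05 threshold (two-sided assumed). Assumed: the within-group correlation r between one covariate and the parameter, and the group difference d in that covariate, in SD units. There is no preeclampsia effect once the covariate is accounted for.

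**Step 1: bias.** The spurious standardised difference is r × d. For r of 0.2 to 0.4 and d of 0.2 to 0.5 this runs from 0.2 × 0.2 = 0.04 SD to 0.4 × 0.5 = 0.20 SD.

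**Step 2: rejection rate of the unadjusted t-test.** Noncentral t with 78 df and noncentrality r × d × √(40/2) = r × d × √20. For r=0.3, d=0.5: 0.3 × 0.5 × 4.472 = 0.671, which gives 10.2%.

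| d | r=0.2 | r=0.3 | r=0.4 |
|---|---|---|---|
| 0.2 | 5.4% | 5.8% | 6.4% |
| 0.3 | 5.8% | 6.8% | 8.3% |
| 0.5 | 7.3% | 10.2% | 14.3% |
| 1.0 | 14.3% | 26.3% | 42.4% |

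The last row is extreme, given the shared eligibility limits. Two covariates at r=0.3 and d=0.5 each give 26.3% if they act in the same direction and 5% if they cancel.

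**Step 3: what d means in years.** If ages spread evenly over 18 to 45, the SD is 27/√12 = 7.8 years, so d=0.5 is 3.9 years. With an assumed SD of 5 it is 2.5 years.

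**Step 4: the adjusted model.** In simulations of 10,000 studies per setting, over 42 settings, linear regression on group plus the covariates rejected in 4.5% to 5.4%, with mean bias within 0.006 SD. With a skewed outcome the rates were 3.9% to 4.8% (ordinary SE), 4.0% to 4.4% (robust SE) and 4.7% to 5.1% (log scale). A factor left out of the model still biases it: at r=0.3, d=0.5 for that factor, it rejects in 10.9%, with bias 0.3 × 0.5 = 0.15 SD.

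**Step 5: precision.** The unadjusted 95% half-width is t(0.975, 78) × √(2/40) = 1.991 × 0.2236 = 0.445 SD. The simulated half-widths with two covariates fitted are:

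- Both d=0.2: 0.374 SD (r=0.4 each) to 0.435 SD (r=0.2 each).
- Both d=0.5: 0.394 SD (r=0.4 each) to 0.458 SD (r=0.2 each), and about 0.48 SD if neither covariate is related to the parameter.
- Both d=1.0, covariates uncorrelated: 0.457 SD (r=0.4 each) to 0.531 SD (r=0.2 each), and 0.554 SD if unrelated to the parameter; 0.554/0.445 = 1.24.
- Both d=1.0, unrelated to the parameter, correlated 0.4 and shifted in opposite directions: about 0.61 SD; 0.61/0.445 = 1.37.

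**The case against.** The strongest reply is that the test is right for what the plan claims. The objective is only to compare findings, and no causal or independent association is asserted. As a contrast of unadjusted group means, the t-test keeps its 5%. Harm needs three things: an imbalance, a covariate that matters, and a reader who attributes the difference to preeclampsia. The documents show none of them, and at small imbalance the inflation is slight. This stands and limits the size of the point. It does not remove the gain from an adjusted estimate, because Section 7 neither labels the comparison as unadjusted nor offers a result that would separate the explanations.

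A second reply is that two covariates are an arbitrary set, now chosen after data collection, and that other factors remain. That is also fair. Adjustment reduces one source of error and does not isolate a preeclampsia effect. The late choice has to be disclosed.

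A third is that gestational age at echo is undefined for a postpartum scan, which the secondary time frame allows. This is correct, and the fix must deal with it.

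A reader might infer that the groups were in fact unmatched. The documents are silent on matching; they do not rule it out.

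**Conclusion.** The point holds as a conditional weakness in one secondary outcome and should be fixed. For r of 0.2 to 0.4, the chance of a spurious significant result rises from 5% to between 5.4% and 8.3% for d of 0.2 to 0.3, and to between 7.3% and 14.3% at d=0.5. Every r and d here is an assumption.

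Two stronger readings are tempting. One is that the comparison is confounded, with false-positive rates of 26% or 42%. Those rates need a 1 SD imbalance in one covariate or, for the 26%, two moderate imbalances acting together, and the documents give no baseline data to support either. The other is that the study's main result is compromised. It is not: the primary outcome is a prevalence within the preeclampsia group and involves no between-group test.

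**What to change.** In Section 7, for secondary outcome 1:

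- Keep the t-test or Mann-Whitney comparison and label it unadjusted and descriptive.
- Beside it, report for each parameter a linear regression on group adjusted for maternal age and gestational age at echo, with the adjusted mean difference and 95% CI. Use a log scale or robust standard errors if the parameter is skewed.
- Restrict these models to antepartum third-trimester scans, and report any postpartum scans separately.
- Tabulate both covariates by group.
- Disclose that the covariates were chosen after data collection, and note residual confounding wherever a difference is linked to preeclampsia.
- If gestational week at echo was not recorded, adjust for maternal age only and say so.
- If matching was done, state the factors and account for them in the analysis.
- If no adjusted model is added, state that the comparison is unadjusted and make no attribution to preeclampsia.

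The cost is SAP wording and four extra models, or five if septal and lateral E' are analysed separately. No new data collection is expected. Maternal age is an eligibility variable. Gestational week at echo is not listed among the data, but the third-trimester and 20-week criteria require pregnancy dating. Enrolment ended in June 2025 and the document is dated August 2025, so matching can no longer be introduced. The precision cost is small unless imbalance is extreme. In that case the interval is up to about 24% wider with uncorrelated covariates, and about 37% wider in the least favourable setting examined.

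### In sparse 2 x 2 tables where the analyst would turn to Fisher's exact test, Boschloo's exact test would usually recover some power at the same 5% level

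*Combined protocol and SAP*

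**What the plan says.** Section 7 (Statistical Analysis Plan) gives one line for all categorical data: they are "compared using Chi-square or Fisher's exact test". The significance level is 0.05. The section states neither sidedness nor a rule for choosing between the two tests, and it gives no expected rates or power.

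The tables concerned are these:

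- **Severity.** Section 7 lists "Subgroup analysis: association between severity of preeclampsia and prevalence of diastolic dysfunction". Section 4 admits preeclamptic women "with or without severity criteria", so this table divides Group A, which section 2 sets at 40 women.
- **Symptoms.** Secondary outcome 2 in section 6 is "Association between diastolic dysfunction and maternal symptoms (dyspnea, palpitations, pulmonary edema"). That makes three tables. The plan does not say whether they use the 40 preeclamptic women or all 80.

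The primary outcome in section 6 is "Prevalence of left ventricular diastolic dysfunction in preeclamptic women", a proportion in one group.

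**The concern.** Fisher's test conditions on both margins of the table. In small tables few p-values are attainable, so its true error rate can lie well below the nominal 5%. The severity and symptom tables hold the fewest women in the study, and a common convention sends such tables to Fisher because an expected count falls below 5. If so, part of an already modest chance of detecting a difference is lost, although an exact test that holds the same level is available.

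Only secondary and subgroup analyses are at stake.

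**Working it through.** The plan has no power or sample-size figure to reproduce, so the check compares the tests directly.

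**Inputs from the document**
- Level 0.05 (section 7).
- 40 women per cohort (section 2).

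**Assumed, because the document is silent**
- Two-sided testing.
- Severity splits of 20/20, 15/25, 10/30 and 8/32.
- Event rates as shown below.
- Prevalence of dysfunction of 25% or 40% for the symptom tables.
- The usual rule: Fisher if any expected count is below 5, otherwise uncorrected chi-square.

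**When the usual rule picks Fisher.** The smallest expected count is (smaller group) x (rarer outcome total) / N.
- 8 v 32: at most 8 x 20/40 = 4, so Fisher is always chosen.
- 10 v 30: at most 10 x 20/40 = 5, so Fisher is chosen unless exactly 20 of the 40 women have the event.
- 15 v 25 at 40% v 10%: the overall rate is (15 x 0.40 + 25 x 0.10)/40 = 0.2125, and 15 x 0.2125 = 3.2. Fisher is chosen in about 98% of samples.
- 20 v 20 at 50% v 20%: the overall rate is (20 x 0.50 + 20 x 0.20)/40 = 0.35, and 20 x 0.35 = 7. Fisher is chosen in about 5% of samples.

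**Error rate.** For a rejection region R, enumerate every table (a, b):

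size(p) = sum over R of C(n1,a) C(n2,b) p^(a+b) (1-p)^(n1+n2-a-b)

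The maximum is taken over a 999-point grid of p. Fisher's R is p < 0.05. Boschloo's R is Fisher p <= c, with c the largest cut-off that keeps the maximum size at or below 0.05 (for 8 v 32, c = 0.082; for 40 v 40, c = 0.071).

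| Split | Fisher, max size | Boschloo, max size | Chi-square, max size |
|---|---|---|---|
| 20 v 20 | 2.5% | 4.6% | 5.3% |
| 15 v 25 | 3.3% | 5.0% | 5.6% |
| 10 v 30 | 2.9% | 4.5% | 5.4% |
| 8 v 32 | 3.2% | 4.9% | 9.1% |
| 40 v 40 | 3.3% | 4.8% | 5.9% |

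**Power.** The same sum, with p1 in the first group and p2 in the second.

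| Table and rates | Fisher | Usual rule | Boschloo | Boschloo minus rule |
|---|---|---|---|---|
| 15 v 25, 40% v 10% | 51.9% | 51.9% | 61.5% | +9.6 |
| 10 v 30, 50% v 20% | 35.4% | 35.4% | 41.4% | +6.0 |
| 10 v 30, 40% v 10% | 47.1% | 47.1% | 53.8% | +6.7 |
| 10 v 30, 30% v 5% | 45.9% | 45.9% | 53.4% | +7.5 |
| 8 v 32, 40% v 10% | 46.5% | 46.5% | 55.7% | +9.2 |
| 8 v 32, 30% v 5% | 44.9% | 44.9% | 48.6% | +3.7 |
| 20 v 20, 50% v 20% | 40.9% | 52.9% | 49.2% | -3.7 |
| 40 v 40, 50% v 20% | 74.9% | 81.7% | 81.0% | -0.7 |

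With very rare events the gain is erratic. At 10 v 30 it is nil for 2% in the 10 against 20% in the 30 (5.0% with either test), and 16.6 points with those rates exchanged (29.6% to 46.2%).

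**Symptom tables with a random split.** The number of women with dysfunction is itself random, so results are averaged over a binomial count.
- N = 40: Fisher's size is 0.6% to 3.1% for symptom rates of 5% to 30%. Power for 40% v 10% rises from 46.7% to 53.2% (dysfunction prevalence 25%) and from 52.9% to 58.4% (40%).
- N = 80: Fisher's size reaches 3.7%. Power for 20% v 5% rises from 44.4% to 48.7% and from 48.2% to 52.3%.

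**Switching rule.** The usual rule has a maximum size of 5.2% at 20 v 20, 5.4% at 15 v 25 and 5.7% at 40 v 40. The same enumeration with Boschloo in place of Fisher inside the rule gives 5.3%, 5.4% and 5.7%. The slight excess comes from the chi-square branch.

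**The case against.** A reader might infer that the plan prescribes Fisher for all these comparisons, so that power is lost throughout and every 2 x 2 table should move to Boschloo. The document does not support that. Section 7 names chi-square as well, and whether expected counts fall below 5 depends on splits and rates it does not give. At 20 v 20 with 50% v 20%, the usual rule has more power than Boschloo (52.9% against 49.2%). In the 40 v 40 comparison it also usually picks chi-square, and Boschloo lowers power: 72.3% to 70.0% for 40% v 15%, and 62.9% to 59.2% for 30% v 10%. Part of the rule's advantage is its slightly excessive size, but no power gain from Boschloo can be claimed there.

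Three further objections stand:

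- **Timing.** Section 3 says the study ran from March to June 2025, and the document is dated August 2025. Moving to a test that rejects more often after data collection needs disclosure.
- **Multiplicity.** One severity and three symptom tests are unadjusted. If all four nulls held, expected false positives would rise from about 4 x 0.03 = 0.12 towards 4 x 0.05 = 0.20.
- **Convention.** Chi-square and Fisher are conventional choices, and Fisher holds its level. Even with Boschloo, power is only about 41% to 62% for the 30-point differences examined in 40 women, so few conclusions are likely to turn on the choice.

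These limit the scope and weight of the point. They do not remove it at 10 v 30, at 8 v 32, or at 15 v 25 with low rates, where the rule almost always leads to Fisher.

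**Conclusion.** The point holds as a modest, optional improvement confined to sparse 2 x 2 tables. Where Fisher would be used in 40-woman tables, its maximum true size is about 2.5% to 3.3%. Boschloo keeps size at or below 5%, typically adds 4 to 10 points of power, and was never less powerful than Fisher in any scenario examined.

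The size of the gain rests on assumed splits, rates, two-sided testing and the expected-count convention. The direction against Fisher did not depend on the split chosen.

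It does not touch the primary single-group prevalence, and it does not serve the ordered severity-by-degree comparison in secondary outcome 3. Nor is it evidence that the plan's tests are invalid.

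**What to change.** In section 7, state that 2 x 2 tables with any expected count below 5 are tested with Boschloo's unconditional exact test (two-sided, 0.05) instead of Fisher's. Keep chi-square for larger or denser tables, including prevalence by group at 40 v 40. This also supplies the missing selection rule and sidedness. The plan must say how women classed as indeterminate enter the dysfunction variable, since the tables are 2 x 2 only once that is settled.

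Boschloo at 40 v 40 as well would hold size at or below 5%, against up to about 5.7% for the usual rule, but would cost about 1 to 4 points of power at moderate rates.

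**Cost.** One line of text and freely available software. The test is less familiar to clinical readers, and the true error per test rises from about 3% towards the nominal 5% across several unadjusted secondary tests. The change must be fixed before these tables are analysed. If analysis has begun, report it as a dated amendment with the originally named test alongside.

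### Secondary outcome 3 asks how preeclampsia severity correlates with the degree of diastolic dysfunction, but the SAP's only severity line concerns prevalence and no ordered measure of association is named

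*Combined protocol and SAP*

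**What the plan says.** Section 6 lists as secondary outcome 3: "Correlation between severity of preeclampsia and degree of diastolic dysfunction". Section 5 classifies diastolic function as Normal, Indeterminate, or "Diastolic Dysfunction (Grade I = impaired relaxation; Grade II = pseudonormal; Grade III = restrictive".

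Section 7 mentions severity once: "Subgroup analysis: association between severity of preeclampsia and prevalence of diastolic dysfunction". That line names no test. Section 6 uses the same word, prevalence, for the primary outcome, "Prevalence of left ventricular diastolic dysfunction in preeclamptic women", where it means the proportion of women with dysfunction.

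The general methods in Section 7 are, for continuous variables, "compared using Student's t-test or Mann-Whitney U test", and for the rest, "Categorical variables expressed as counts (%) and compared using Chi-square or Fisher's exact test". No correlation coefficient, trend test or ordinal model appears.

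On severity itself, Section 4 says only that Group A is enrolled "with or without severity criteria". The expected split is not given, and neither is the scale on which severity is recorded.

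**The concern.** The outcome and its analysis target different quantities. Outcome 3 is about how far dysfunction has progressed as severity rises. The severity line is about whether dysfunction is present. If severe and non-severe women have dysfunction equally often but at different grades, the severity line finds nothing, although that is a relation outcome 3 is meant to describe.

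The general rule for categorical variables reduces the gap without closing it. A chi-square or Fisher test on the full severity-by-class table can detect differing grades, but it treats the grades as unordered labels. Its p-value is the same whether severe women have the higher or the lower grades, and it gives no size of correlation. The one rank test in the SAP is assigned to continuous variables.

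At stake is whether the result reported for outcome 3 is the quantity that outcome 3 names. With no method fixed, the yes/no split, the table test, a rank test and the placing of Indeterminate all remain open choices.

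**Working it through.** The documents give no figure to reproduce: 40 women per cohort is stated without rates, effect size or power. The check is a side-by-side reading plus an illustration on assumed counts.

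**Side by side**

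| | Section 6, outcome 3 | Section 7, severity line |
|---|---|---|
| Quantity | correlation | association |
| Diastolic variable | degree | prevalence |
| Method | none named | none named; chi-square/Fisher by the general rule |

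**Worked table.** Group A has 40 women (Section 2). The 20/20 severity split and all counts are assumed, with no Indeterminate women.

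| | Normal | I | II | III |
|---|---|---|---|---|
| Non-severe | 8 | 9 | 2 | 1 |
| Severe | 8 | 2 | 3 | 7 |

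1. *Yes/no.* Dysfunction is present in 12/20 and 12/20, so p = 1.00.
2. *Full-table chi-square.* Expected counts per row are 8, 5.5, 2.5 and 4. The statistic is 0 + 2(3.5²/5.5) + 2(0.5²/2.5) + 2(3²/4) = 4.45 + 0.20 + 4.50 = 9.15 on 3 df, p = 0.027. Fisher's exact p = 0.024.
3. *Kendall's tau-b, all classes.* For each severe woman, count non-severe women in a lower class minus those in a higher class, then sum: 8(−12) + 2(8−3) + 3(17−1) + 7(19) = −96 + 10 + 48 + 133 = 95. Pairs untied on severity: 20×20 = 400. Pairs untied on class: 780 − (120+55+10+28) = 567. Tau-b = 95/√(400×567) = **+0.20**. The rank-sum variance with ties is (400/12)(41 − 6024/1560) = 1237.9, so z = 47.5/35.18 = 1.35, p = 0.18.
4. *Kendall's tau-b, Grades I–III only.* The sum is 2(−3) + 3(9−1) + 7(11) = −6 + 24 + 77 = 95. Pairs untied on severity: 12×12 = 144. Pairs untied on class: 276 − (55+10+28) = 183. Tau-b = 95/√(144×183) = **+0.59**. The variance is (144/12)(25 − 1944/552) = 257.7, so z = 47.5/16.05 = 2.96, p = 0.003.
5. *Exchange the labels of Grades I and III.* The chi-square and Fisher p-values do not change. Tau-b becomes −0.20 and −0.59.

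**Simulated rejection rates** (20/20 split, two-sided 0.05, every input assumed).

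*Relation in grade only.* Grade mix I/II/III is 70/25/5% non-severe and 20/45/35% severe, and 20% of women without dysfunction are Indeterminate. Prevalence is 25, 40 or 60% in both groups.

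| Test | 25% | 40% | 60% |
|---|---|---|---|
| Yes/no chi-square | 5% | 5% | 5% |
| Five-class chi-square | 14% | 29% | 52% |
| Rank test, Indeterminate omitted | 6% | 10% | 27% |
| Exact rank test, Grades I–III only | 23% | 49% | 73% |

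*Difference in prevalence only* (25 v 55%, 25 v 60%, 20 v 50%; grade mix 60/28/12% in both groups). The rank test with Indeterminate omitted rejects in 42/53/46%, against 49/61/53% for yes/no chi-square.

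The yes/no test stays at its false-positive rate when only grade differs. The rank test over all classes is not generally stronger than the tests the SAP already lists.

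**The case against.** **The SAP already covers it.** Diastolic class is categorical, so a severity-by-class table with counts, percentages and a chi-square or Fisher test is within Section 7. This stands to a large extent. A reader might infer that the plan cannot show the direction of the relation. It can: the percentages would show which group has the higher grades. What remains missing is a single ordered measure of the correlation, with its uncertainty.

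**Degree need not mean grade.** The documents never define it, and the study also records continuous diastolic measures, for which Section 7 names tests. This stands as a caution. Grades I–III are the natural reading, but it is an inference. The severity scale is equally unsettled, so no one coefficient can be called the only correct one.

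**An ordered test may do worse.** This stands. In the worked table the rank test over all classes misses the relation (p = 0.18) that full-table chi-square finds (p = 0.027). If only prevalence differs, the rank test loses 7 to 8 points to yes/no chi-square. A reader might infer that an ordinal analysis would gain power; the calculations do not support that. The comparison among graded women shows a grade relation most directly and belongs beside the all-class analysis.

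**The wording is merely loose.** With severity in two categories, a correlation is in practice a two-group comparison. That may be so, but the diastolic variable still differs between the two sections.

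**Conclusion.** The mismatch holds on the text: outcome 3 concerns degree, the only severity line concerns prevalence, and no ordered measure is named. It is a point to consider, limited to one secondary outcome in 40 women. The primary outcome and secondary outcomes 1 and 2 are unaffected.

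The conclusion rests on two readings: that degree means Grades I–III, and that prevalence means dysfunction present or absent, as in the primary outcome. The documents give no prevalence, grade mix, severity split or Indeterminate rate, so the worked counts and simulated rates are illustrations and not estimates for this study.

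The document is dated August 2025, after the stated study period, "over a 5-month period from March 2025 to June 2025". A reader might infer that the severity line was chosen after seeing results. Nothing in the documents shows that; the dates only mean that an addition made now must be labelled honestly.

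**What to change.** Keep the prevalence line and add to Section 7, with its date and a label saying that it was specified after the stated study period:

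> Secondary outcome 3 (Group A): the full severity-by-class table (counts, %) is shown with a chi-square or Fisher test. The ordered association of severity (with/without severity criteria, or the recorded scale if graded) with diastolic class is reported as Kendall tau-b with 95% CI and a rank-sum p-value (the tau-b test if severity is graded), both over Normal < I < II < III and among women with Grades I–III. All-class results are shown with Indeterminate omitted, merged with Normal, and placed between Normal and Grade I.

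Showing all three treatments of Indeterminate avoids choosing a rule that the documents do not contain.

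Rewording outcome 3 to prevalence is not an equal alternative. It would change an outcome to fit its analysis after the stated study period.

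**Cost:** a little more analysis on variables the plan already collects. Intervals will be wide: the simulated half-width for tau-b at n = 40 was about 0.25 to 0.32. The comparison among graded women rests on fewer still, about 10 to 24 in the assumed scenarios. Omitting Indeterminate removes about 3 to 6 women in those scenarios.
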